#### **OVERALL RATIONALE FOR PROTOCOL AMENDMENT 07**

This protocol amendment updates the primary analysis for the randomized assessment in Part 2. Additional analysis on baseline serum IL-8 (sIL-8) data suggested an association with tumor burden, decreasing the relevance of using sIL-8 as a selection biomarker. Thus, the primary analysis population was changed from to all randomized participants. To facilitate a timely analysis, the primary endpoint was further revised to objective response rate (ORR). Approximately participants (in each treatment arm) currently enrolled in Part 2 will provide a sufficient sample size to analyze the new primary endpoint of ORR under a statistical framework

Additionally, for Part 2,

objectives and endpoints no longer considered essential for the study analysis have been reclassified as exploratory.

Additional changes are made to simplify study procedures for participants following the final analysis. These changes aim to alleviate participant and site burden and remove sample collections and study procedures that are no longer considered necessary. Assessments and procedures deemed necessary for monitoring the safety of the subjects remain unchanged.

SUMMARY OF KEY CHANGES FOR PROTOCOL AMENDMENT 07		
Section Number & Title	Description of Change	Brief Rationale
Title Page	Updated the clinical scientist and clinical trial physician/medical monitor information.	Administrative change.
	Removed the EudraCT identifier and updated the European Union trial number.	The term "EudraCT" is obsolete, as it refers to the previous European legislation.
Section 1: Protocol Summary	Updated to reflect changes made in the body of the protocol.	To align with protocol updates.

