# 4 OBJECTIVES AND ENDPOINTS

Table 4-1: Objectives and Endpoints - Part 1

Objectives	Endpoints
Primary	
To characterize safety, tolerability, and DLTs, and to determine the RP2D of BMS-986253 administered in combination with nivolumab, or in combination with nivolumab and ipilimumab in participants with advanced solid tumors.	Incidence of AEs, SAEs, AEs meeting protocol- defined DLT criteria, and AEs leading to discontinuation, death, and laboratory abnormalities.
Secondary	

 
To evaluate the preliminary efficacy of BMS-986253 in combination with nivolumab in participants with advanced solid tumors using RECIST v1.1.
 
To characterize the PK and immunogenicity of BMS-986253 when administered in combination with nivolumab, or in combination with nivolumab and ipilimumab in participants with advanced solid tumors.
 
To assess serum IL-8 levels at baseline (ie, screening) and changes in IL-8 levels on treatment.
 
	
 
ORR and DOR per RECIST v1.1 per investigator.
 
Summary measures of PK parameters and incidence of ADA to BMS-986253.
 
Summary measures of IL-8 and change (or percent change) from baseline in IL-8 on treatment.
 

Abbreviations: ADA, anti-drug antibody; AE, adverse event; DLT, dose-limiting toxicity; DOR, duration of response; EOT, end of treatment; ORR, objective response rate; PK, pharmacokinetic(s);

Protocol Amendment No.: 07

RECIST, Response

Evaluation Criteria in Solid Tumors; RP2D, recommended Phase 2 dose; SAE, serious adverse event.

[figure not shown]
Table 4-2: Objectives and Endpoints - Part 2

	Objectives	Endpoints
Pri	imary	
•	To compare the ORR of BMS-986253 plus nivolumab plus ipilimumab with placebo plus nivolumab and ipilimumab using RECIST v1.1.	ORR based on BICR assessments per RECIST v1.1 in all randomized participants.
Sec	condary	
•	To estimate PFS of BMS-986253 plus nivolumab plus ipilimumab and placebo plus nivolumab and ipilimumab in participants with advanced melanoma using RECIST v1.1 (regardless of baseline serum IL-8 levels).	mPFS and PFS hazard ratio based on BICI assessments per RECIST v1.1.
•	To compare the safety of BMS-986253 plus nivolumab plus ipilimumab with placebo plus nivolumab plus ipilimumab in participants with advanced melanoma.	discontinuation, death, and laborator

Protocol Amendment No.: 07

Date: 17-May-2024 68

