# 5.4.1 Rationale for Targeting IL-8 in Cancer

IL-8 (CXCL8) is a chemokine whose main physiologic function is the attraction of a polymorphonuclear inflammatory leukocyte infiltrate acting on CXCR1/2. Recently, it has been found that tumors frequently produce IL-8, which exerts different pro-tumoral functions, including

Protocol Amendment No.: 07

angiogenesis, provide growth factors and survival signaling for CSCs as well as the attraction of immunosuppressive myeloid cells endowed with the ability to dampen anti-tumor immunity. In the tumor, IL-8 is mainly produced by cancer cells themselves. IL-8 serum concentration has been shown to correlate with cumulative tumor size, stage, and prognosis in numerous cancer types.  Because of a short concentrations closely follow in time the changes occurring in IL-8-producing cells. Recent data strongly support a correlation between serum IL-8 levels and tumor burden as well as clinical stage in patients with melanoma, RCC, NSCLC, and HCC.  In fact, patients with higher serum IL-8 levels had worse overall survival (OS). Because of the roles that IL-8 plays in favoring tumor progression through several mechanism such as modulating chemotaxis, resistance to therapy, angiogenesis, and metastasis, therapeutic strategies aiming to interfere with IL-8 has the potential to alleviate these functions, thereby diminishing the risk of (further) metastatic spread and recurrent disease in these patients. Anti-IL-8 neutralizing antibody (HuMax-IL-8) was shown to decrease IL-8-induced neutrophil activation and migration in vitro resulting in beneficial anti-inflammatory responses in patients with palmoplantar pustulosis which also provided support to test this antibody in cancer patients.

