If PK, pharmacodynamic, and/or safety analyses indicate further assessment of a dosing regimen is not warranted and/or assessment of additional dosing regimens is indicated, then randomization will be stopped, and subsequent participants will be assigned sequentially to dosing regimens available at that time. If any dosing regimen evaluates a higher dose of BMS-986253 than previously explored, an initial 4-participant safety lead-in with a 28-day DLT period will be required. Approximately participants will be dosed in the dosing regimen(s) of interest. Additional exploration of a specific dosing regimen may be warranted, in which case a maximum of approximately additional participants will be assigned to a dosing regimen of interest in Part 1B. A maximum of approximately participants will be dosed in Part 1B.

Part 1C is a safety evaluation of BMS-986253 in combination with nivolumab and ipilimumab. Part 1C will begin once the DLT period is completed for Cohort 1B6 (BMS-986253 3600 mg Q2W + nivolumab 480 mg Q4W), and will enroll simultaneously with Part 1B. In Part 1C, participants

Protocol Amendment No.: 07 Date: 17-May-2024

Protocol Amendment No.: 07

#### Part 2

Part 2 will begin after determination of the RP2D from Part 1 and generating safety data on the triplet combination of BMS-986253 plus nivolumab plus ipilimumab in Part 1C. Part 2 is a double-blind randomized evaluation of BMS-986253 plus nivolumab plus ipilimumab versus placebo plus nivolumab plus ipilimumab and will be conducted to evaluate the efficacy of BMS-986253 in participants who are refractory to anti-PD-(L)1 therapy.

IRT will be used to track the enrollment number.

Once assigned a subject ID in IRT, participants that have met all eligibility criteria will be randomized through IRT (up to 3 days prior to C1D1). The following information is required prior to participant randomization:

- Participant subject ID
- Date of birth
- Gender
- Screening serum IL-8 level

• Screening LDH

Participants will be randomized in a 1:1 ratio to treatment and control arms. Three stratification factors will be used during randomization: screening

and screening LDH (≤ ULN or > ULN). Screening serum IL-8 data will be transferred directly from the analyzing laboratory to IRT. BRAF status and screening LDH must be entered in eCRF by the site.

Approximately participants will be randomized in Part 2.

The exact procedures for using the IRT will be detailed in the IRT manual.

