# Table 10.3.1-2: Part 2 Efficacy Analysis

BICR-assessed PFS	The estimate of the PFS hazard ratio between treatment groups will be calculated using a
PFS is defined as the time from first dose to the date of first objectively documented progression, per RECIST v1.1, or death due to any cause, whichever occurs first. Clinical deterioration in the absence of objectively documented progression per RECIST v1.1 is not considered progression for the purpose of determining PFS. Participants who die without a reported progression will be considered to have progressed on the date of their death. Participants who did not progress or die will be censored on the date of their last evaluable tumor assessment. Participants who did not have	stratified with treatment and stratification factors as covariates. A two-sided 95% CI for the hazard ratio will also be presented.  The PFS curves for each treatment group will be estimated using product limit method and will be displayed graphically. Median PFS with corresponding two-sided 95% CI in each treatment group will be computed via the log-log transformation method.
any on study tumor assessments and did not die will be censored on the date of first dose. Participants who started any subsequent anticancer therapy, including tumor-directed radiotherapy and tumor-directed surgery, without a prior reported progression will be censored at the last evaluable tumor assessment prior to initiation of the subsequent anticancer therapy. The PFSR at time T is defined as the probability that a participant has not progressed and is alive at time T following first dose.	PFS rates at fixed time points (eg, 3, 6, 9 months, depending on the minimum follow-up) will be presented along with their associated 95% CIs. These estimates will be derived from estimate and corresponding CIs will be derived based on for variance derivation and on log-log transformation applied to the survivor function.

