#### 4 BASELINE DOCUMENTATION OF 'TARGET' AND 'NON-TARGET' LESIONS

When more than one measurable lesion is present at baseline all lesions up to a maximum of five lesions total (and a maximum of two lesions per organ) representative of all involved organs should be identified as target lesions and will be recorded and measured at baseline (this means in instances where patients have only one or two organ sites involved a maximum of two and four lesions respectively will be recorded).

Note: A maximum of two lesions can be selected per organ system. For example, a maximum of two lung lesions can be selected (selected from one lung or one lesion from each). A maximum of two lymph nodes can be selected at baseline, as the lymphatic system is considered one organ.

Target lesions should be selected on the basis of their size (lesions with the longest diameter), be representative of all involved organs, but in addition should be those that lend themselves to reproducible repeated measurements. It may be the case that, on occasion, the largest lesion does not lend itself to reproducible measurement in which circumstance the next largest lesion which can be measured reproducibly should be selected.

A sum of the diameters (longest for non-nodal lesions, short axis for nodal lesions) for all target lesions will be calculated and reported as the baseline sum diameters. If lymph nodes are to be included in the sum, then as noted above, only the short axis is added into the sum. The baseline sum diameters will be used as reference to further characterize any objective tumor regression in the measurable dimension of the disease.

All other lesions (or sites of disease) including pathological lymph nodes should be identified as non-target lesions and should also be recorded at baseline. Measurements are not required and these lesions should be followed as 'present', 'absent', or in rare cases 'unequivocal progression' (more details to follow). In addition, it is possible to record multiple non-target lesions involving the same organ as a single item on the case record form (eg, 'multiple enlarged pelvic lymph nodes' or 'multiple liver metastases').

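### The visible PFS model leaves out baseline tumour burden, which the trial already records; if burden is prognostic, this pulls the hazard ratio toward 1, though it does not widen the confidence interval

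*Combined protocol and SAP*

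**What the plan says.** Table 10.3.1-2 (Section 10.3.1) estimates the BICR-assessed PFS hazard ratio from a model with "treatment and stratification factors as covariates". The model's name is blacked out. The table adds: "A two-sided 95% CI for the hazard ratio will also be presented". No PFS test or alpha is visible. Table 4-2 words the secondary objective as "To estimate PFS of BMS-986253 plus nivolumab plus ipilimumab and placebo plus nivolumab and ipilimumab", and PFS is the only time-to-event endpoint visible among the Part 2 secondary endpoints.

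Section 7.4 states: "Participants will be randomized in a 1:1 ratio to treatment and control arms". It continues: "Three stratification factors will be used during randomization". Screening IL-8 and LDH (split at the upper limit of normal) are visible. The third factor appears to be BRAF status, but the text is partly redacted.

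On burden, the Amendment 07 rationale says that further baseline serum IL-8 data "suggested an association with tumor burden, decreasing the relevance of using sIL-8 as a selection biomarker". Section 5.4.1 says: "Recent data strongly support a correlation between serum IL-8 levels and tumor burden as well as clinical stage". Section 6.1 requires radiographically measurable disease. Appendix 8, section 4, has the target-lesion diameters summed at baseline and explains: "The baseline sum diameters will be used as reference to further characterize any objective tumor regression in the measurable dimension of the disease".

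**The concern.** Section 5.4.9 chose the stratification factors to limit imbalance in variables that may affect efficacy. Tumour burden is not visibly one of them, and it is not visibly in the PFS model. Chance imbalance in burden is therefore handled neither by design nor by analysis, except for whatever part IL-8 and LDH carry.

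A proportional hazards model that omits a prognostic variable also estimates a treatment hazard ratio closer to 1 than the one conditional on that variable, even with perfect balance. Amendment 07 fixes Part 2 at the participants already enrolled, so recruitment cannot make up for this. The missing variable needs no new data collection.

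**Working it through.** There is no planned figure to reproduce: the Part 2 sample size is redacted, and no PFS event count, assumed hazard ratio or effect of burden on PFS is visible. The size was therefore simulated.

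**Inputs, all assumed.** A Cox model, because a hazard ratio is estimated; 40, 60 or 80 participants per arm at 1:1; true PFS HR 0.65 (log HR -0.431); burden HR per SD of 1.0, 1.25, 1.5 or 2.0; correlation of burden with the two-level IL-8 and LDH factors of 0.3 or 0.6; IL-8 HR 1.3; LDH HR 1.4; no BRAF effect; about 65-139 events. This makes 3 x 4 x 2 = 24 scenarios of 1,000 trials each, with Monte Carlo error of about 1.6 points on each percentage.

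**Models.** A: treatment plus the three stratification factors. B: A plus baseline burden.

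Results at 60 per arm (correlation 0.3 / 0.6):

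| Burden HR per SD | Mean log HR, A | Mean log HR, B | SE, A | SE, B | CI excludes 1, A (%) | CI excludes 1, B (%) |
|---|---|---|---|---|---|---|
| 1.0 | -0.454 / -0.437 | -0.458 / -0.440 | 0.205 / 0.205 | 0.207 / 0.207 | 60.6 / 56.5 | 60.4 / 56.3 |
| 1.25 | -0.423 / -0.436 | -0.439 / -0.451 | 0.206 / 0.206 | 0.208 / 0.208 | 56.2 / 55.2 | 58.2 / 57.9 |
| 1.5 | -0.409 / -0.411 | -0.442 / -0.442 | 0.207 / 0.208 | 0.209 / 0.210 | 52.0 / 50.6 | 55.7 / 54.8 |
| 2.0 | -0.363 / -0.368 | -0.444 / -0.434 | 0.209 / 0.210 | 0.213 / 0.214 | 40.0 / 43.0 | 52.7 / 52.9 |

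**CI width.** Take burden HR 1.5 and correlation 0.3. The width on the log scale is 2 x 1.96 x 0.207 = 0.811 for A and 2 x 1.96 x 0.209 = 0.819 for B, so B is slightly wider. The mean SE was larger with burden in all 24 scenarios, by about 0.5-2%, and the empirical SD was larger in 22 of 24.

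**Attenuation.** In the same row, exp(-0.409) = 0.66 for A and exp(-0.442) = 0.64 for B. At burden HR 2.0, exp(-0.363) = 0.70 and exp(-0.444) = 0.64.

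**Hand check.** The chance that the CI excludes 1 is roughly Φ(|log HR|/SE - 1.96). For A, 0.409/0.207 = 1.976, giving Φ(0.016) = 51%. For B, 0.442/0.209 = 2.115, giving Φ(0.155) = 56%. The simulation gave 52.0% and 55.7%.

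**Change from A to B over all three sizes.** Burden HR 1.0: about 0 points. 1.25: 0 to +3. 1.5: +3 to +9. 2.0: +6 to +14 (largest 51.9% to 65.8%, at 80 per arm).

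**Second set.** 1,500 trials per setting; true HR 0.67; burden log HR 0.25-0.4 per SD, that is HR exp(0.25) = 1.28 to exp(0.4) = 1.49; correlation 0.5. At log HR 0.4, adding burden moved the chance that the CI excludes 1 from 31% to 35% at n=80, 42% to 49% at n=120 and 53% to 60% at n=160. At log HR 0.25 the full model, which also made IL-8 and LDH continuous, gained about 2-7 points. In the log HR 0.4 settings, making IL-8 and LDH continuous once burden was in added about 1 point (36%, 50% and 61%).

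**Type I error.** With no treatment effect, both models rejected 5.8% in the first set. In the second, all models rejected about 6-7%. Adjustment makes no difference.

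**The case against.** The plan's choice is conventional and valid. It adjusts for the randomization factors, and IL-8 and LDH may already carry part of the burden information. PFS is secondary with an estimation objective, so power is not its natural yardstick. The burden-adjusted hazard ratio is also a different, more conditional quantity, so its distance from 1 is not simply a gain in information. Part of the table is redacted, and Section 10.3 calls itself a summary of a SAP still to be finalised before database lock, so a supportive model may be intended. All of this stands. It limits the point to an improvement rather than an error, but the reported hazard ratio is the secondary result and its attenuation still matters.

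Four stronger readings are tempting and are not supported.

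- A reader might infer that IL-8 stands in for tumour burden. The Amendment 07 rationale reports an association, and uses it to argue about IL-8 as a selection biomarker. Section 5.4.1 reports a correlation. Section 5.4.7 describes IL-8 as tracking outcome independently of baseline burden in tumour types that include melanoma.
- A reader might infer that omission loses precision. For a hazard ratio the standard error moves slightly the other way.
- A reader might infer a much larger gain. A run of only 400 trials at n=120 gave 37% to 52%, a rise of 15 points, but the same run gave 26% to 33% at n=80 and 49% to 56% at n=160, 7 points each. Larger runs at n=120 with the same range of burden effects gave about 0-8 points.
- A reader might infer that IL-8 and LDH should also become continuous. That adds about 1 point or less, departs from the factors as randomized, and needs a rule for IL-8 values too low to quantify.

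**Conclusion.** The point holds as a modest, inexpensive improvement. The visible PFS model omits a baseline variable that the trial already records and that is plausibly prognostic. If it is prognostic, the strata-only hazard ratio is pulled toward 1 and its 95% CI excludes 1 less often. The central range is about 2-8 points for a burden log hazard ratio of 0.25-0.4 per SD and 80-160 participants; single simulated settings ran from 0 to 9. The difference is nil if burden has no effect and reaches about 14 points at a hazard ratio of 2.0 per SD. Sample size, effect sizes and correlations are all assumptions. The strata-only analysis remains valid, and its interval is not wider for omitting burden.

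**What to change.** Before unblinding, add to the SAP a PFS model with treatment, the stratification factors as randomized, and log baseline sum of diameters. Report it beside the strata-only model, and say in advance which of the two leads.

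State whose baseline reading is used: BICR would match the endpoint, and the investigator's is the alternative. Give one simple rule for a missing sum, for example the median over both arms combined, and apply the same rule where the chosen reader finds no target lesion, since a zero sum has no logarithm.

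The cost is SAP wording and one more coefficient. The hazard ratio becomes conditional on one more covariate, log-linearity in burden is assumed, and the missing-value rule has to be fixed in advance. If it is left until after unblinding, any adjustment for burden will be post hoc.

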# 10.3.2 Safety Analyses

All safety analyses for will be performed on the treated population.

Endpoint	Statistical Analysis Methods
Incidence of AEs, SAEs, AEs meeting protocoldefined DLT criteria, AEs leading to discontinuation, deaths AEs will be graded according to CTCAE v4.03.	DLT rate by dose level; Frequency distribution of treated participants with AE using the worst CTC grade. Participants will only be counted (1) once at the PT level, (2) once at the SOC level, and (3) once in the 'Total participants' row at their worst CTC grade, regardless of SOC or PT.
Laboratory abnormalities Laboratory values will be graded according to CTCAE v4.03.	Laboratory shift table using the worst CTC grade on treatment per participant

Protocol Amendment No.: 07

Abbreviations: AE, adverse event; CTC, Common Terminology Criteria; CTCAE, Common Terminology Criteria for Adverse Events; DLT, dose-limiting toxicity; PT, Preferred Term; SAE, serious adverse event; SOC, System Organ Class.

# 10.3.3 Pharmacokinetic Analyses

Endpoint	Statistical Analysis Methods
Cmax, AUC(0-T), AUC(TAU), Ctau, CLT, Css-avg, AI_AUC, AI_Cmax, AI_Ctau, T-HALF	Summary statistics: geometric means and coefficients of variation
Tmax	Summary statistics: medians and ranges
Ctrough	Summary statistics to assess attainment of steady state: geometric means and coefficients of variation; plots vs time by dose

Abbreviations: AI\_AUC, AUC Accumulation Index; AI\_Cmax, Cmax Accumulation Index; AI\_Ctau, Ctau Accumulation Index; AUC(0-T), area under the plasma serum concentration-time curve from time zero to time of last quantifiable concentration; AUC(TAU), area under the serum concentration-time curve in 1 dosing interval; CLT, total body clearance; Css-avg, average serum concentration over a dosing interval (AUC[TAU]/tau) at steady state; Ctau, observed serum concentration at the end of a dosing interval; Tmax, Time of maximum observed plasma serum concentration; Ctrough, trough observed serum concentrations (this includes pre-dose concentrations [C0] and Ctau). Note: PK time-concentration data may be pooled with data from other studies for PPK analysis, which will be

# 10.3.4 Immunogenicity Analyses

presented in a separate report.

Endpoint	Statistical Analysis Methods	
Incidence of ADA to BMS-986253, nivolumab, or ipilimumab administrated in combination	Frequency distribution of baseline ADA-positive participants and ADA-positive	
Baseline ADA-positive participant is defined as a participant who has an ADA detected sample at baseline. ADA-positive participant is a participant with at least 1 ADA-positive sample relative to baseline after initiation of the treatment	participants after initiation of the treatment; summary of ADA peak titer, ADA onset and duration, summary of select AEs by ADA status, summary of BOR by ADA status	

Abbreviation: ADA, anti-drug antibody; AE, adverse event; BOR, best overall response.

